## 7. STATISTICS

A Statistical Analysis Plan (SAP) will be finalized before database lock. The plan will detail the implementation of the statistical analyses in accordance with the principle features stated in the protocol.

### 7.1. Determination of Sample Size

The sample size of the study was determined based on the precision of the estimate of the treatment effect for the primary endpoint – the percent change from baseline in UPCR from a 24-hour urine sample at Week 32. It should be noted that geometric mean ratio of UPCR at Week 32 to baseline is statistically equivalent to mean of the change from baseline in logarithm of UPCR. Therefore, the effect size of the study is defined as the difference of change from baseline between cemdisiran and placebo in the logarithm of UPCR.

Based on the [\[Fellstrom 2017\]](#) study, we assume that in the placebo arm the geometric mean ratio of UPCR at Week 32 to baseline is 0.88 (log standard deviation [SD] 0.597), corresponding to a 12% reduction, while the geometric mean ratio is 0.5, or a 50% reduction for the cemdisiran arm. Using these assumptions, sample size of 9 and 18 in the placebo and cemdisiran arms will provide a width of 0.80 ( $\pm 0.4$ ) for the 90% confidence interval (CI) for treatment effect size estimate (cemdisiran – placebo) in log scale.

### 7.2. Statistical Methodology

The statistical and analytical plans presented below are brief summaries of planned analyses. More complete plans will be detailed in the statistical analysis plan (SAP). Changes to the

methods described in the final SAP will be described and justified as needed in the clinical study report. For information on study endpoints, see Section 2.

Descriptive statistics including the number of patients, mean, median, standard deviation (SD), interquartile range (Q1, Q3), minimum, and maximum values will be presented for continuous variables. Frequencies and percentages will be presented for categorical and ordinal variables.

Additional data summaries to help understand any impact of COVID-19 on PK/PD, efficacy and safety assessments will be outlined in the SAP.

### **7.2.1. Populations to be Analyzed**

The following populations will be analyzed:

- Modified Intent-to-treat (mITT): All patients who receive any amount of study drug and have at least one post baseline assessment in proteinuria. Patients will be grouped by assigned treatments (ie, as randomized).
- Safety Analysis Set: All patients who received any amount of study drug. Patients who received any amount of cemdisiran will be included in the cemdisiran arm. Patients in the Safety Analysis Set will be grouped by treatment received.
- PK Analysis Set: All patients who receive a full dose of study drug and have at least one postdose blood or urine sample for PK concentration.
- PD Analysis Set: All patients who receive a full dose of study drug and who have at least one postdose blood sample for the determination of plasma C5 level.

The primary population used to evaluate efficacy will be the mITT Population. Safety will be analyzed using the Safety Analysis Set. The PK and PD Analysis Sets will be used to conduct PK and PD analyses, respectively.

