### 3. INVESTIGATIONAL PLAN

#### 3.1. Summary of Study Design

This is a multicenter, double-blind, placebo-controlled study comprised of three periods ([Figure 1](#)). The first period of the study is an observational 14-week run-in period during which patients' blood pressure, kidney function, degree of hematuria, and proteinuria will be measured. Patients will not receive study drug (cemdisiran or placebo) during this time. The standard of care is expected to remain unchanged during this run-in period. The second study period is a 36-week treatment period which will evaluate the efficacy and safety of SC cemdisiran compared to SC placebo in combination with standard of care in patients with IgAN and persistent proteinuria. The third period of the study is a 156-week optional OLE period to further evaluate the long-term safety and clinical activity of cemdisiran. During the OLE, all patients (including those initially on placebo) will be treated with cemdisiran in combination with standard of care.

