The study will include a Screening period of up to 120 days to determine eligibility of patients and to complete disease-related assessments. The Investigator will notify the Sponsor before screening patients to allow an assessment of the ability of the site and new trial participants to comply with the protocol given limitations during the COVID-19 pandemic. Patients will provide written informed consent and visit the study site approximately 2 weeks before starting the run-in period to complete the protocol screening assessments. Following successful screening, the 14-week run-in period will commence, during which patients' blood pressure, kidney function, degree of hematuria, and proteinuria as well as treatment with standard of care will be documented by the Investigator. The standard of care is expected to remain unchanged during this run-in period. Patients whose proteinuria level remains  $\geq 1$  g/24-hours within 2 weeks of the end of the run-in period, and who meet blood pressure and eGFR criteria will be eligible to enroll in the 36-week treatment period. Upon confirmation of eligibility followed by vaccination against meningococcal infections, patients will be randomized at a 2:1 ratio to receive 600 mg of cemdisiran or placebo every 4 weeks in combination with standard of care. Approximately 30 patients are planned to be randomized in total, 20 in the cemdisiran arm and 10 in the placebo arm. Patients excluded before randomization will be replaced at screening.

During the run-in period, patients will visit the study site 14, 8, and 2 weeks prior to randomization (Weeks 0, 6, and 12 of the run-in period). If a run-in visit cannot proceed according to schedule, it may be delayed up to 28 days, with subsequent visits being rescheduled based on the new date. Visit windows, as indicated in the Schedule of Assessments ([Table 1](#)), are applied to the rescheduled date. Approval from the Medical Monitor is required prior to initiation of the treatment period. If a patient cannot proceed to the treatment period as planned, the run-in period can be extended as needed. If the final run-in visit will not be within 56 days of randomization, this visit will be repeated, and the new visit will serve as the Week -2 visit to determine eligibility for randomization.

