##### **Recording Adverse Events**

The Investigator is responsible for recording all SAEs and only AEs related to study procedures that are observed or reported by the patient during the run-in period (before the administration of the first dose of study drug) regardless of their relationship to study drug through the end of study. All AEs, including non-serious AEs, occurring after signing of the ICF and before study drug administration will be captured as medical history (see Section 6.1). All AEs will be collected starting after administration of the first dose through the end of the safety follow-up period. Non-serious AEs will be followed until the end of study.

The Investigator is responsible for recording SAEs that are observed or reported by the patient after the time when the informed consent is signed regardless of their relationship to study drug through the end of study. SAEs will be followed until satisfactory resolution, until baseline level is reached, or until the SAE is considered by the Investigator to be chronic or the patient is stable, as appropriate.

All AEs must be recorded in the source records for the clinical study site and in the eCRF for the patient, whether or not they are considered to be drug-related. Each AE must be described in detail: onset time and date, description of event, severity, relationship to study drug, action taken, and outcome (including time and date of resolution, if applicable).

For SAEs, record the event(s) on both the eCRF and the SAE form.

For AEs that are considered AEs of clinical interest (Section 6.7.6.1), the supplemental AEs of Clinical Interest eCRF should be completed. Additional clinical and laboratory information may be collected. Refer to CRF completion guidelines for details on reporting events in the supplemental AEs of Clinical Interest eCRF.

For all ISRs, the Investigator, or delegate, should submit a supplemental ISR eCRF, recording additional information (eg, descriptions, onset and resolution date, severity, treatment given, event outcome).

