### 7.2.5.3. Exploratory Endpoints

Change from baseline in exploratory efficacy variables will be summarized. Percent of patients in full clinical remission and incidence of ADA will be tabulated by treatments.

The slope of eGFR for the double-blind period will be estimated for each treatment and the slope of eGFR for the entire study period including the OLE will be analyzed. Other inferential statistics for exploratory efficacy variables may be presented as needed. Details will be described in the SAP.

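### The Safety Analysis Set rule has no period limit, so placebo patients who enter the open-label extension move to the cemdisiran arm along with their placebo-period events

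*Protocol*

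**What the plan says.** Section 7.2.1 (Populations to be Analyzed) includes in the Safety Analysis Set everyone who received any study drug, groups patients by treatment received, and adds: "Patients who received any amount of cemdisiran will be included in the cemdisiran arm". The Statistical Methods part of the synopsis carries the same rule. Neither place limits it to a study period. Section 7.2.8 (Safety Analyses) then assigns all safety analyses to this set.

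Three other provisions meet this rule:

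- Section 3.1 makes the OLE optional and states: "During the OLE, all patients (including those initially on placebo) will be treated with cemdisiran in combination with standard of care". The first OLE dose is given at Week 36.
- Section 6.7.6.2 (Recording Adverse Events) states: "All AEs will be collected starting after administration of the first dose through the end of the safety follow-up period". The collection window therefore runs across the switch.
- Section 7.2.8 summarises adverse events after the first dose of study drug as numbers and percentages of patients. Its laboratory shift tables run from a baseline on or before Study Day 1 to the worst value. No cut or new baseline at the switch is stated.

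The planned size is given in section 3.1: "Approximately 30 patients are planned to be randomized in total, 20 in the cemdisiran arm and 10 in the placebo arm".

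**The concern.** An as-treated rule of this kind normally serves to place a patient who was dosed in error. Here it also applies to every placebo patient who takes up the OLE, because each of them receives some cemdisiran. Such a patient belongs to the cemdisiran arm from then on, and nothing in the text leaves the first 36 weeks under placebo.

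Frequency of adverse events is a secondary endpoint (section 2), and section 1.3 justifies the placebo arm partly by the better assessment of safety that it allows. The controlled safety evidence in this trial is about 10 placebo patients over the double-blind period. A rule that empties that group, and counts its events against the drug, removes the comparison the arm was included to provide. Those left under placebo would also be a selected group: the patients who declined the extension or stopped early.

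**Working it through.** **The plan's own figure.** The only related calculation in the protocol is the precision statement in section 7.1. Inputs: log SD 0.597, and 9 placebo and 18 cemdisiran patients.

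Half-width of the 90% CI = 1.645 × 0.597 × √(1/9 + 1/18) = 0.401, so the width is 0.802.

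This agrees with the plan ("sample size of 9 and 18 in the placebo and cemdisiran arms will provide a width of 0.80"). It concerns Week 32, before any switch, in a population grouped as randomised. The safety rule does not touch it.

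**Head count under the rule as written.** Inputs: 20 cemdisiran and 10 placebo patients (section 3.1). OLE uptake among placebo patients is not stated, so it is varied. If m of the 10 enter, the arms become 20 + m and 10 − m.

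**Placebo time relabelled.** Assume every patient completes the 36 weeks. Relabelled placebo time is 36m patient-weeks. The enlarged cemdisiran arm has 36(20 + m) patient-weeks in the blinded period, so the share that is really placebo time is m/(20 + m).

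| Assumed uptake | m | Cemdisiran vs placebo | Placebo patient-weeks relabelled | Share of the cemdisiran arm's blinded time |
|---|---|---|---|---|
| 0% | 0 | 20 vs 10 | 0 | 0% |
| 50% | 5 | 25 vs 5 | 180 | 180/900 = 20% |
| 80% | 8 | 28 vs 2 | 288 | 288/1008 = 29% |
| 100% | 10 | 30 vs 0 | 360 | 360/1080 = 33% |

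**Effect on a blinded-period rate difference.** Let the true event rates be c on cemdisiran and p on placebo, and assume that placebo patients who enter the OLE have the same rate as those who do not. The relabelled cemdisiran rate is (20c + mp)/(20 + m). Subtracting p gives [20/(20 + m)] × (c − p). The true difference shrinks to 20/25 = 80% of its value at 50% uptake and to 20/28 = 71% at 80% uptake. At 100% there is no comparator.

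**Unequal follow-up.** If percentages are taken over all collected data, a patient who does not enter the OLE contributes up to 36 + 52 = 88 weeks, and an OLE completer up to 188 + 52 = 240 weeks. With the same constant event rate for both, incidence = 1 − exp(−rate × weeks/52). The rates are assumptions.

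| Events per patient-year | 88 weeks | 240 weeks | Gap |
|---|---|---|---|
| 1.0 | 82% | 99% | 17 points |
| 0.3 | 40% | 75% | 35 points |
| 0.1 | 16% | 37% | 21 points |

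This gap arises with no drug effect. It is the reason to use exposure-adjusted rates wherever the two periods are combined.

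**The case against.** The strongest reply is that the intended meaning can be recovered. Section 3.1 has patients from the two treatment arms entering the OLE, so the arms exist before it, and the rule reads naturally as a provision for dosing errors. Section 7.2 calls its text a brief summary, and section 7.2.8 leaves further detail to the SAP, where separate double-blind and OLE tables would be usual. Safety is descriptive, and an independent data monitoring committee reviews unblinded data.

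Much of that stands as to intent and weight, but it does not remove the defect. The protocol is not silent here: it states a grouping rule and applies it to all safety analyses, and section 7 asks the SAP to follow the protocol's main features. A SAP that grouped by period would depart from 7.2.1 as worded. The protocol does set period limits elsewhere, as section 7.2.5.3 does for the double-blind eGFR slope.

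Two stronger readings are tempting and are not supported:

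- **eGFR.** A reader might infer from "the slope of eGFR for the entire study period including the OLE will be analyzed" that one straight line is fitted through the switch and the control comparison is lost. No passage states that model. Section 7.2.5.3 leaves the details to the SAP and separately estimates the double-blind slope for each treatment, so that comparison is kept.
- **A larger exposure gap.** A reader might compare 36 with 188 weeks and, at 1 event per patient-year, obtain 50% versus 97%, a gap of 47 points. That leaves out the 52-week safety follow-up, during which adverse events are still collected. With it, the windows are 88 and 240 weeks and the gap at that rate is 17 points. Nor does the protocol say outright that percentages are pooled over the whole study.

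**Conclusion.** The safety arm rule is wrong as written. Taken literally, it moves each placebo patient who enters the OLE, with that patient's placebo-period adverse events and laboratory shifts, into the cemdisiran arm. It leaves 5, 2 or 0 controls at an assumed 50%, 80% or 100% uptake, and 20% to 33% of the cemdisiran arm's blinded-period time would then be placebo time.

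The sizes rest on the planned 20 and 10 patients, completion of 36 weeks by all, and uptake figures that are assumptions. The literal reading rests on none of these: it needs only one placebo patient to enter the OLE. The point is confined to safety. The primary endpoint at Week 32 is analysed as randomised and precedes the switch, and no sample-size figure changes.

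**What to change.** In section 7.2.1 and in the synopsis:

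1. For the controlled safety comparison, define the arm as treatment received during the double-blind period: any cemdisiran before the first OLE dose means the cemdisiran arm. This keeps the provision for dosing errors.
2. Use the same window in both arms: from first dose to the first OLE dose, or to the Week 36 visit for patients who do not enter the OLE. Running non-entrants on into safety follow-up would make the windows unequal again.
3. Summarise data on cemdisiran across both periods separately, counting each patient from the first cemdisiran dose, with exposure-adjusted rates.
4. Show safety follow-up separately.

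The cost is wording in two places, matching text in the SAP and one more set of safety tables. No new data are needed.

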### **7.2.2. Examination of Subgroups**

Subgroup analyses may be conducted for selected endpoints. Detailed methodology will be provided in the SAP.

### **7.2.3. Handling of Missing Data**

Handling of missing data will be described in the SAP.

### **7.2.4. Baseline Evaluations**

Demographics and other baseline characteristics, including disease-specific information, will be summarized descriptively by treatment arm and overall for the mITT and Safety Analysis Set.

Baseline value for 24-hour UPCR will be calculated as the average of two valid 24-hour urine assessments before randomization (at the Week -2 visit).

## 7.2.5. Efficacy Analyses

### 7.2.5.1. Primary Endpoint

The primary endpoint of the study is the percentage change from baseline in 24-hour UPCR at Week 32. The 24-hour UPCR will be log transformed for analyses. The primary analysis will be performed using a restricted maximum likelihood (REML) based Mixed-Effect Model Repeated Measures (MMRM) approach. The outcome variable is change from baseline in 24-hour UPCR in log-scale at the Week 16 and Week 32 visits. Analysis will include fixed effects of treatment (cemdisiran vs. placebo), scheduled visits (Week 16 and Week 32), interaction term of treatment and scheduled visits, baseline 24-hour UPCR in log-scale (continuous), and patient as a random effect. The least square mean difference and its 90% confidence interval will be estimated. In addition, placebo-adjusted geometric mean percent change at the Week 32 visit and its 90% CI will be presented.

A sensitivity analysis for the impact of missing data and the normality assumptions on the log-transformed UPCR data will be performed. Details will be provided in the SAP.

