### **3.5. Method of Assigning Patients to Treatment Groups**

Using the Interactive Response System (IRS), patients will be randomized 2:1 to the cemdisiran or placebo arms. Randomization will be stratified by baseline urine proteinuria levels ( $\geq 1$  g/24h and  $< 2$  g/24h versus  $\geq 2$  g/24h).

Each patient will be uniquely identified in the study by a combination of the site number and patient identification number. Upon signing the informed consent form (ICF), the patient will be assigned a patient identification number by the IRS. The Investigator or his/her designee will contact the IRS after confirming that the patient fulfills all the inclusion criteria and none of the exclusion criteria at Screening and prior to randomization.

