### 7.2.5.2. Secondary Efficacy Endpoints

The secondary efficacy endpoints include percent change from baseline in 24-hour proteinuria (g/24 hours) at Week 32, percent of patients with partial clinical remission (UP <1.0 g/24-hours), percent of patients with >50% reduction in 24-hour proteinuria, change from baseline in UPCR as measured in a spot urine at Week 32 and change from baseline in hematuria at Week 32.

The percentage of patients with partial clinical remission or with >50% reduction in 24-hour proteinuria for each treatment arm and the difference between treatment arms will be presented together with an approximate 90% confidence interval based on Wilson score method.

Change from baseline in UP in 24-hour urine assessments and UPCR by spot urine at Week 32 will be analyzed similarly to the analysis of the primary variable as appropriate. The descriptive statistics for change from baseline in hematuria (urine dipstick) at Week 32 will be provided.

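### Randomisation is stratified by 24-hour proteinuria, but neither the primary MMRM nor the partial-remission comparison uses the stratum (minor: a mismatch between analysis and design, not a material loss of precision)

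*Protocol*

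**What the plan says.** Section 3.5 of the protocol: "patients will be randomized 2:1 to the cemdisiran or placebo arms", and "Randomization will be stratified by baseline urine proteinuria levels", with the cut at 2 g/24 h. Section 3.1 gives the size: "Approximately 30 patients are planned to be randomized in total, 20 in the cemdisiran arm and 10 in the placebo arm".

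Section 7.2.5.1 specifies the primary MMRM: "Analysis will include fixed effects of treatment (cemdisiran vs. placebo), scheduled visits (Week 16 and Week 32), interaction term of treatment and scheduled visits", then "baseline 24-hour UPCR in log-scale (continuous), and patient as a random effect". The result is an estimate with an interval: "The least square mean difference and its 90% confidence interval will be estimated". The randomisation stratum is not among the terms.

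Section 7.2.5.2 covers partial remission and the >50% reduction endpoint. After the percentage in each arm, "the difference between treatment arms will be presented together with an approximate 90% confidence interval based on Wilson score method". No baseline or stratum adjustment is mentioned.

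**The concern.** Stratified randomisation forms two groups and allocates 2:1 within each. The natural analysis keeps those groups. Here the primary model uses a related covariate instead: 24-hour protein depends on creatinine excretion as well as on UPCR, so log UPCR does not reproduce the stratum exactly.

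The gap is plainer for partial remission. That endpoint is a fixed threshold of 1 g/24 h on the variable used to stratify, so a patient's stratum largely sets how far protein must fall. Section 7.2.1 also limits the efficacy population to dosed patients with a post-baseline proteinuria assessment, and the sample-size section counts on 27 patients out of 30. A few exclusions can disturb the balance that randomisation created, and nothing in the remission comparison would correct for it.

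**Working it through.** **1. The protocol's own precision figure.** Inputs from section 7.1: log SD 0.597, with 9 placebo and 18 cemdisiran patients.

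Half-width = 1.645 × 0.597 × √(1/9 + 1/18) = 1.645 × 0.597 × 0.4082 = 0.401, so the width is 0.802. The stated 0.80 reproduces. It comes from an unadjusted two-sample standard error and takes no credit for either a covariate or the stratum. (With t on 25 df the width is 0.833.)

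**2. Price of the extra term.** Treat Week 32 as a single-visit ANCOVA in 27 patients. Residual df are 27 − 3 = 24 with treatment and log UPCR, and 23 with the stratum added. The 95th percentile of t moves from 1.711 to 1.714, a factor of 1.002.

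**3. Effect on the primary interval.** The check used 4,000 simulated trials per scenario, with 2:1 permuted blocks within strata and complete data. The documents do not give the baseline distribution, the correlation between 24-hour protein and UPCR, or the prognostic slopes. Assumed ranges: median protein 1.6 to 2.5 g before truncation at 1 g, log SD 0.5 to 0.8, correlation 0.5 to 0.9. Mean 90% half-widths with 30 patients:

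| Week 32 change depends on | log UPCR only | log UPCR + stratum | Ratio |
|---|---|---|---|
| baseline UPCR | 0.386 | 0.389 | 1.008 |
| UPCR and 24-hour protein | 0.380 | 0.380 | 1.002 |
| neither | 0.394 | 0.398 | 1.010 |
| stratum, extra 0.3 log effect | 0.397 | 0.391 | 0.986 |
| stratum, 0.5 log effect, correlation 0.5 | 0.391 | 0.361 | 0.923 |

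With 27 patients, the four scenarios without a separate stratum effect moved from 0.407 to 0.413, 0.411 to 0.415, 0.401 to 0.402 and 0.419 to 0.424: factors of 1.002 to 1.015. The planned model covered at about 0.90, rising to 0.92 only in the most extreme case.

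**4. Why the stratum predicts remission.** Section 7.1 assumes for placebo that the "geometric mean ratio of UPCR at Week 32 to baseline is 0.88 (log standard deviation [SD] 0.597"), and a ratio of 0.5 for cemdisiran. Assume the same ratios and SD hold for 24-hour protein in both arms, whatever the baseline. A patient starting at B g remits with probability Φ[(ln(1/B) − ln(ratio)) / 0.597].

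- B = 1 g: placebo Φ(0.1278/0.597) = Φ(0.214) = 0.58; cemdisiran Φ(0.6931/0.597) = Φ(1.161) = 0.88.
- B = 2 g: placebo Φ((−0.6931 + 0.1278)/0.597) = Φ(−0.947) = 0.17; cemdisiran Φ(0) = 0.50.

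The lower stratum therefore lies between 0.17 and 0.58 on placebo and between 0.50 and 0.88 on cemdisiran. The upper stratum lies at or below 0.17 and 0.50. With an assumed median of 2 g and log SD 0.5, the stratum averages are about 0.33 against 0.07 on placebo and 0.68 against 0.28 on cemdisiran.

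**5. Size of an imbalance.** With those averages, moving one of 9 placebo patients to the other stratum shifts the expected placebo rate by (0.33 − 0.07)/9 = 0.029. One of 18 on cemdisiran shifts that arm by (0.68 − 0.28)/18 = 0.022. The planned Wilson-type interval averages 0.540 wide in the same setting, so a one-patient imbalance is small beside it.

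**6. Intervals for remission.** Across the assumed baselines, the planned interval covers 0.91 to 0.93. A stratified Newcombe-Wilson interval is 1% to 4% wider (0.540 to 0.552 in the setting above). A Mantel-Haenszel interval with Sato variance is 2% to 13% narrower than planned, but covers only 0.85 to 0.87 against a nominal 0.90.

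**The case against.** The strongest reply is that nothing is lost. Continuous log UPCR carries most of what a two-level proteinuria cut can say, stratified allocation already limits imbalance, and the planned remission interval is safe. Section 7.2 calls the stated methods brief summaries, so the SAP, which is not shown, may add the stratum. On precision this reply stands. It does not answer the mismatch: the protocol lists its model terms, log UPCR is not the stratification variable, and the remission comparison has no baseline adjustment of any kind.

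Three stronger readings are tempting and should not be drawn.

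- A reader might infer that the intervals are wider than the design earns. The 0.80 width never relied on adjustment, and in ordinary scenarios the extra term leaves the primary interval unchanged or slightly wider. For remission, one example gives a variance of 0.0295 unstratified and 0.0258 within strata, a standard-error ratio of √(0.0258/0.0295) = 0.935. That is not a gain to be collected. Because allocation is stratified, the two estimators vary almost equally (sampling SD 0.153 for both in one simulated setting, 0.175 against 0.174 in another), and step 6 shows that no well-calibrated interval becomes shorter.
- A reader might extend the point to the >50% reduction endpoint. That threshold is relative to baseline, so it is not tied to the 2 g cut, and stratifying it widens the interval by 1% to 2%.
- A reader might note that the superseded Amendment 2 synopsis included the stratification factor and infer that it was dropped by mistake. That model had a different endpoint and analysis, and a difference from superseded text is not an error.

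**Conclusion.** The point holds as a minor one. The listed primary model and the partial-remission comparison do not use the groups by which patients are randomised. For remission the stratum is prognostic almost by construction. The benefit of including it is agreement between analysis and design, and protection against stratum imbalance after exclusions in about 27 to 30 patients.

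No material gain in precision should be claimed. The primary half-width changes by about −1% to +1.5% in ordinary scenarios; the 8% narrowing needs an assumed 0.5 log stratum effect and a correlation of only 0.5 between 24-hour protein and UPCR. No bias or under-coverage of the planned analyses was found. These sizes rest on the assumed baseline distribution, correlation and slopes, on a complete-data ANCOVA standing in for the MMRM, and on applying the UPCR effect assumptions to 24-hour protein.

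**What to change.** In section 7.2.5.1, add the two-level randomisation stratum as a fixed effect beside log baseline UPCR. In section 7.2.5.2, keep the planned Wilson interval as the main result for partial remission and add a supportive Mantel-Haenszel risk difference across the two strata. State the variance method, and note that the supportive interval may under-cover at this sample size. Leave the >50% reduction analysis as it is.

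The cost is one degree of freedom (t from 1.711 to 1.714 with 27 patients), one added sentence in each section and one extra table line. No data collection or sample size changes. If the SAP already contains the stratum term, aligning the protocol's list of model terms with it settles the primary part.
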